4.3 JUSTIFICATION FOR DOSE

Using low-frequency (LF) rTMS is thought to decrease cortical excitability. In schizophrenia, Hoffman et al. (1999) were the first to introduce rTMS for the treatment of refractory AVH in treatment-resistant patients. The authors used LF rTMS over the left temporo-parietal junction (TPJ) and showed significantly reduced AVH severity with effects lasting up to 15 weeks. Yet, daily administration of rTMS over the course of several days without antipsychotic medication could comprise risks, especially for patients suffering from additional psychotic symptoms.

Therefore, the crucial next step is, firstly, to explore the effects of rTMS in medication-free individuals in the initial phase of psychosis and, secondly, to use an accelerated protocol of only one day with four sessions of rTMS. The reduced time of rTMS administration would diminish potential risks related to other psychotic symptoms and reveal rTMS effects on AVH within a few days.

4.4 END OF STUDY DEFINITION

A participant is considered to have completed the study if he or she has completed all phases of the study including the last visit or the last scheduled procedure shown in the Schedule of Activities (SoA), Section 1.3. The end of the study is defined as completion of the last visit or procedure shown in the SoA in the trial globally.

5 STUDY POPULATION

5.1 INCLUSION CRITERIA

In order to be eligible to participate in this study, an individual must meet all of the following criteria:

1. Provision of signed and dated informed consent form
2. Stated willingness to comply with all study procedures and availability for the duration of the study
3. Male or female, aged 18 to 65
4. Diagnosed with DSM V diagnosis of schizophrenia (295.90), schizoaffective disorder (295.70), or brief psychotic disorder (298.80), prone to AVH in the acute phases of the disorder

5. Willing to adhere to the rTMS regimen
6. Subtherapeutic antipsychotic serum level upon admission as per Nathan Kline Institute reference guidelines on antipsychotic therapeutic serum levels.
7. Agreement to adhere to Lifestyle Considerations (see section 5.3) throughout study duration

5.2 EXCLUSION CRITERIA

An individual who meets any of the following criteria will be excluded from participation in this study:

1. Therapeutic level of antipsychotic medication
2. ECT or rTMS within three months (see the TMS screening questionnaire)
3. History of seizures
4. Presence of implanted electronic device or metal implant in the head and neck region (DBS, cochlear implant, etc.)
5. Pregnancy, as assessed with a pregnancy test prior to every MRI measurement, or lactation
6. Any active general medical condition or CNS disease which can affect cognition or response to treatment
7. Treatment with another investigational drug or other intervention within 2 weeks
8. Current diagnosis of delirium, dementia, or amnestic amnesiac disorder; Diagnosis of mental retardation; Current (within the past three months) diagnosis of active substance dependence, or active substance abuse within the past week as indicated by self-report.
9. Patients who are cognitively impaired and are thus not able to give informed consent

Note, that other medication such as antidepressant, pain killers, or sleep medication are no exclusion criteria per se. Yet, if these medications are needed for the treatment of other mental illnesses such as subsumed under point 5 or 7 of the exclusion criteria then patients cannot be included in the study.

5.3 LIFESTYLE CONSIDERATIONS

During this study, participants are asked to

- Participants who use tobacco products will be instructed that use of nicotine-containing products (including nicotine patches that are available as per standard clinical care) in the 2 hours prior to the MRI measurement on Day 1 and 3 are not allowed.
- Abstain from caffeine- or xanthine-containing products (e.g., coffee, tea, and cola drinks) for 2 hours before each imaging measurement (Day 1 and 3).
- Abstain from alcohol the evening before the start of the study until after collection of the final imaging data.

Note, that participants are not asked to abstain from antipsychotic medication if they wish to take it or in case of an emergency. Yet, no treatment with antipsychotic medication from the study's start until completion of the study is one of the main inclusion criteria and violation of this criterion will lead to exclusion from the study. See section 2.2.1 "Known Potential Risks" for more information on risks and section 5.5 "Strategies for Recruitment and Retention" for further information on recruitment.

5.4 SCREEN FAILURES

Screen failures are defined as participants who consent to participate in the clinical trial but are not subsequently randomly assigned to the study intervention or entered in the study. A minimal set of screen failure information is required to ensure transparent reporting of screen failure participants, to meet the Consolidated Standards of Reporting Trials (CONSORT) publishing requirements and to respond to queries from regulatory authorities. Minimal information includes demography, screen failure details, eligibility criteria, and any serious adverse event (SAE).

Individuals who do not meet the criteria for participation in this trial (screen failure) because of a no suffering from AVH may be rescreened at a later date. Rescreened participants should be assigned the same participant number as for the initial screening.

5.5 STRATEGIES FOR RECRUITMENT AND RETENTION

This is an exploratory pilot study to test the efficacy of rTMS for the treatment of AVH in patients with schizophrenia spectrum disorder. Thus, we aim to recruit 20 patients per group (active *versus* sham rTMS) to determine the treatment's efficacy.

Both male and female patients with a schizophrenia spectrum disorder, who are referred for standard care treatment and who express interest in an additional day of rTMS treatment before the start of antipsychotic treatment, will be recruited for the study.

Patients will be approached by trained staff of the study and asked about their AVH symptoms. In the case that patients report hearing voices (which is not always the case), we will propose rTMS as a novel, potentially beneficial treatment option for AVH, as confirmed by meta-analysis that found significant effect sizes ranging from 0.4 to 1 depending on the publication (Aleman et al., 2007; Demeulemeester et al., 2012; Freitas et al., 2009; C. Slotema et al., 2012), compared to conventional antipsychotic medication. Especially, if the hallucinations are the symptom that predominantly cause the suffering, then rTMS may lead to symptom reduction and may have a lower risk for potential side effects than the treatment with antipsychotics.

We will not try to dissuade patients who want to take antipsychotic medication from taking medication. Our aim is to convincingly explain the advantages of rTMS as a novel treatment with a promising potential. Antipsychotic medication can be given after completion of the study or at any point during the study in the case of an adverse event (see section 8.3.4 "Time Period and Frequency for Event Assessment and Follow-up" for more information), or patients request, but that would mean termination from the study.

For recruitment, we consider all patients suffering from AVH who are not currently on antipsychotics. The patients' history of antipsychotic medication is not in the focus. We will include patients with a first-episode psychosis, patients who did have antipsychotic medication in the past, patients who decline antipsychotic medication.

Recruitment will occur at The Zucker Hillside Hospital from the inpatient unit at Northwell Health. The Zucker Hillside Hospital is the major psychiatric facility associated with the health system. Subjects will be recruited from the inpatient and outpatient units. Prospective subjects will be approached for study enrollment by the psychiatrists who participate in this study and/or a research fellow. Upon subject's agreement, a meeting with the research staff will be scheduled to begin the informed consent process.

The consent process begins with an assessment of the patient's ability to give informed consent. Patients who on initial evaluation by the study investigator are deemed not to be capable of giving informed consent will not be evaluated further. Patients who are deemed capable of giving informed

consent will then be provided with a full and complete description of the study. Capacity will be determined by treating physician prior to the consent process. The capacity assessment will be a brief form checked and signed by the physician who is treating the subject. This form will be kept in the study chart of each subject. The patient will be provided with ample opportunity to review the consent and have all their questions addressed prior to completing enrollment. Written consent will be obtained prior to the commencement of study procedures.

Consent will follow IRB approved procedures. Consent will be obtained by the PI, [name], the study's MD, [name], and the study coordinator, [name]. Consent for patients will occur on the inpatient units of the Zucker Hillside Hospital at MRI.

In order to ensure that subjects understand the fundamental aspects of the study, we require that they demonstrate this by correctly answering a series of specific questions about the study covering key aspects of the study. These Study Information Reviews are IRB approved. The format of the Study Information Review is a question followed by two possible answers. The answers are written in a parallel sentence structure to minimize reading difficulty. We employ the parallel answer format instead of a true false format because of our experience that subjects with limited education and test taking skills better comprehend the parallel answer format.

An example of part of a Study Information Review is presented below.

DIRECTIONS: Below are questions that people frequently have about the study. Each question is followed by 2 answers. One answer is correct and the other answer is wrong. Please put a check mark next to the correct answer.

Question 1. Do I have to be in the study to get treatment at the hospital?

- a) To get treatment, I must be in the study.
OR
- b) To get treatment, I do not have to be in the study.

Question 2. If I start in the study, can I leave before it is over?

- a) If I decide to be in the study, I must stay until it is over.
OR
- b) If I decide to be in the study, I can leave any time that I wish.

Question 3. How long does the study last?

- a) If I want to, I may be in the study for up to 3 days.
OR
- b) If I want to, I may be in the study for up to 3 weeks.

Subjects must answer correctly all the questions on the Study Information Review before providing informed consent for the study. Informed consent will be documented when the subject signs the consent form that has been approved by the Institutional Review Board.

The study purpose, procedures, risks, benefits, and alternatives will be discussed. After informed consent is signed, eligibility will be confirmed by diagnostic and psychometric assessments by trained raters as described in the screening visit. Additionally, we will measure blood levels of antipsychotics to confirm that patients are antipsychotic-free. Based on our previous experience in enrolling patients in other trials, we anticipate that we can accomplish the recruitment goal of forty patients over the course of one year in the proposed study.

Patients will be paid \$ 120 in total for their time and travel expenses for being in this study. If they do not complete the entire study, they will be paid for the number of completed visits. Payment will be made at the end of the study or when patients end their participation.

If the total payment received from Northwell Health, during this year, is equal to \$600 or more, the payment is required to be reported to the IRS. Although this study does not pay \$600, if patients participate in other Northwell Health studies, it is possible their payment could end up totaling \$600. If this occurs, the payment received on this study will be reported to the IRS. In this case, patients will be issued a 1099 form and be required to provide their social security number at that time for reporting purposes. Patients will also be responsible for reporting this income while filing your tax return.

Compensation

	Screening Day	Baseline Assessment	Treatment Day	Follow-up Assessment
Visits	Visit 1	Visit 2	Visit 3	Visit 4
Procedures				
rTMS	None	None	Any weekday	None
MRI	None	1 st at baseline	None	2 nd after rTMS
Clinical Assessment & blood work	Yes	Yes	Yes	Yes
Compensation	\$20	\$50	\$0	\$50

Note that the Screening Day is not specifically set. This day can either be on the first day of the study such that patients who are willing to participate could start immediately with the baseline measurements. While patients who are for example recruited in the evening would have their first day of the study on the following day. In the special case of enrollment on a Friday, the start of the study would be the following Monday. Thus, patients would have to declare that they do not want to take antipsychotics during the weekend and the time of the study. See section 2.3.1 “Known Potential Risks” for information.

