- Male and female subjects 18 to 65 years of age
- DSM V diagnosis of schizophrenia (295.90), schizoaffective disorder (295.70) or brief psychotic disorder (298.80) confirmed by SCID-V interview currently experiencing AVH in the acute phases of the disorder as assessed with the revised Beliefs About Voices Questionnaire (BAVQ-R).
- Patient agrees to rTMS for AVH treatment for 1 day before standard medication therapy.
- Right-handedness assessed with the Edinburgh Handedness Inventory
- Patient is competent to provide informed consent
- Inpatient at the Zucker Hillside Hospital
- No history of seizures

Phase:

N/A

**Description of
Sites/Facilities Enrolling
Participants:**

Participants will be recruited through the Zucker Hillside Hospital in-patient clinic. Recruitment will only take place at this site and no sites outside of the United States are included.

**Description of Study
Intervention:**

All patients receive 1Hz of rTMS over the Sylvian parietal temporal area (area Spt) four times on 1 day (1 pulse/second and a total of 1'000 pulses: 16 minutes' protocol at 100% of motor threshold modified based on

Hoffman et al. (1999)). Area Spt will be localized via baseline structural imaging and our Localite TMS navigation system.

Subjects will be withdrawn from the study if side effects become limiting, or if either the patient or principal investigator determine that rTMS should be discontinued.

[figure not shown]
Study Duration: 18 months in total including 12 months for recruitment and measurements plus 6 months for data analysis.

Participant Duration: Each participant is enrolled for up to 4 days of measurements (minimum of 3 days).

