1.3 SCHEDULE OF ACTIVITIES (SOA)

Visit	Screening	Enrollment/Baseline Assessment	Treatment Day	Follow-up Assessment
Procedures				
Informed consent	X			
Demographics	X			
Medical history	X			
Blood sample	X			
Randomization	X			
TMS screening questionnaire	X			
Administer study intervention			X	
Adverse event review and evaluation	X	X	X	X
Imaging assessment	X	X		X
Complete Case Report Forms (CRFs)	X	X	X	X

Note that the Screening Day is not specifically set. This day can either be on the first day of the study such that patients who are willing to participate could start immediately with the baseline measurements. While patients who are for example recruited in the evening would have their first day of the study on the following day. In the special case of enrollment on a Friday, the start of the study would be the following Monday. Thus, patients would have to declare that they do not want to take antipsychotics during the weekend and the time of the study. See section 2.3.1 "Known Potential Risks" for information.

Only for eligible patients for which an extra vial of blood was not collected for the measurement of serum level of antipsychotic, phlebotomy will be performed especially for this study in order to obtain the blood sample necessary to assess the serum antipsychotic concentration prior to the scanner.

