2.2 RISK/BENEFIT ASSESSMENT

2.2.1 KNOWN POTENTIAL RISKS

AVH symptomatology

Immediate risk

- Auditory verbal hallucinations can have different qualities such as being commenting, commanding, and/or threatening (e.g. harming oneself and others). These qualities can change over time and are thought to be related to factors such as stress (Upthegrove et al., 2016). AVHs during a phase of florid psychosis can have a more threatening character which in turn can lead to more stress and more psychotic symptoms. Therefore, a close monitoring of the patients' hallucinations, well-being, and the content of the AVH is important. All study personnel are trained to detect signs of stress in patients and worsening of psychotic symptoms. Additionally, the Believes About Voices Questionnaire (BAVQ-R) will be given to patients at every visit to assess the content, severity, and distress associated with AVH. Patients will be asked to report about their AVH's content and will be encouraged by the study coordinator to talk about changes in their mood and AVH content.
- In case a patient shows worsening of psychotic symptoms or, in the worst case, gets suicidal or homicidal within the three days of the study, participation is terminated and appropriate actions are initiated in accordance with the ward such as the application of antipsychotic medication given by the patient's treating clinician as per standard treatment guidelines and based on their best judgment. For this reason, the study staff will be in constant contact with the unit staff and the treating physician of the patient to work together with the best clinical interest for the patients' health.

Long-range risks

- There are no known long-range risks

Blood sample

Immediate risks

- We will obtain a blood sample to assess the serum concentration of the antipsychotic at the moment of hospitalization by adding an extra tube to the 2 that are routinely obtained via simple venipuncture as part of routine care in the emergency room. No phlebotomy will be performed at this point with a research indication if there is no clinical indication as per routine care. The additional blood sample will be collected in a third tube (approximately 2-3 mLs) from the same venipuncture for all patients that are hospitalized and potentially eligible to participate in the study. Therefore, the additional tube that is needed for the study does not constitute an additional risk.

Long-range risks

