8 STUDY ASSESSMENTS AND PROCEDURES

8.1 EFFICACY ASSESSMENTS

Rating

All assessments will be performed by trained raters.

Time frame

Screening procedures / evaluation must be done on the same day or the day before inclusion of the patient into the study. The reason for this is that we assess rTMS effect independently of potentially influencing antipsychotic medication effects. Therefore, patients cannot start with antipsychotic medication treatment parallel to the rTMS treatment. Clinical interviews will be conducted by trained staff.

Imaging

MRI acquisition will consist of the following: On the day of imaging, the patient will be transported to the North Shore University Hospital 3T Siemens Prisma MRI suite. The patient will undergo an approximately 55 minutes long acquisition session. All subjects will receive structural (e.g., T1) and functional (e.g. resting BOLD fMRI, DTI, and ASL) MRI exams. During the anatomical images, the participating subject will be asked not to move, during resting state fMRI, the subject will be asked to open their eyes and to think of nothing in particular, but to stay awake. The total scanning time will be approximately 55 minutes.

Assessment of instruments

The primary outcome measure is the improvement of AVH measured with the HCS.

The secondary outcome measures are:

- Qualitative outcome of the BAVQ-R
- AVH as part of positive symptoms measured with the respective BPRS-subscale
- Global functioning assessed using the CGI and GAF
- Cognitive functioning assessed using the rBANS

Structural and functional neurophysiological characteristics are investigated as predictors for rTMS treatment response.

Outcome criteria

Responder criteria:

- a. Clinically significant improvement is defined as a score of <8 on the HCS (Hoffman et al., 2013)
- b. Drop-outs: defined as patients who discontinue treatment before completing the 4 rTMS sessions.

Premature exits:

- a. Consent for study participation is withdrawn before 4 rTMS treatments have been administered, or
- b. rTMS is discontinued for clinical or other reasons before 4 rTMS have been administered, or
- c. Patient misses more than two treatments in total.

Both drop-outs and premature exits in this study will be analyzed as last observation carried forward.

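### The consent check gives three days as the longest study participation, but the synopsis allows four and the Friday enrolment rule spans six calendar days if visits are consecutive

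*Combined protocol and SAP*

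**What the plan says.** Section 5.5 shows a sample of the Study Information Review. Question 3 asks how long the study lasts and offers two answers: "If I want to, I may be in the study for up to 3 days", or the same sentence with three weeks. The section then makes the form a condition of consent: "Subjects must answer correctly all the questions on the Study Information Review before providing informed consent for the study".

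Other places give a length or a window:

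- Section 1.1 (Synopsis, Participant Duration): "Each participant is enrolled for up to 4 days of measurements (minimum of 3 days").
- Section 2.2.1, on a patient who worsens: if the patient "gets suicidal or homicidal within the three days of the study, participation is terminated".
- Section 5.3 restricts nicotine "in the 2 hours prior to the MRI measurement on Day 1 and 3 are not allowed", so baseline imaging is Day 1 and the second scan is Day 3.
- Section 1.3, repeated under the compensation table in 5.5: "Note that the Screening Day is not specifically set". It may coincide with the first study day or come earlier. The same note adds: "In the special case of enrollment on a Friday, the start of the study would be the following Monday". These patients must declare that they do not want antipsychotics over the weekend and during the study. For the risk, the note points to section 2.3.1.
- Section 8.1 (Time frame): "Screening procedures / evaluation must be done on the same day or the day before inclusion of the patient into the study". The reason given is to keep the rTMS effect separate from antipsychotic effects.

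The schema in 1.2 and the compensation table in 5.5 both list four visits, with consent at Visit 1 and baseline at Visit 2.

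**The concern.** The consent check states as a maximum what the synopsis states as a minimum. The length of participation matters more here than in most trials. Sections 2.1 and 4.3 treat time without antipsychotic medication as a risk and justify a one-day treatment schedule by keeping that time short. Section 5.5 describes the review questions as covering the fundamental aspects of the study. A patient who gives the required answer is told a shorter period than the plan permits, and the gap is widest for those who enrol on a Friday.

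The Friday case also exposes two loose ends. Section 8.1 sets a tight screening window measured to a point called inclusion, which is never defined. And the reader is sent for the weekend risk to a section number that is not in the document.

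**Working it through.** **1. Reproduce the synopsis range.** Baseline, treatment and follow-up are separate visits. The Day 1 and Day 3 numbering in 5.3 puts them on three successive days, with screening not counted.

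- Screening on the baseline day: 3 days.
- Screening the day before: 1 + 3 = 4 days.

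This gives 3 to 4 days, as the synopsis says.

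**2. Compare with Question 3.** The stated maximum is 3 days. It equals the synopsis minimum and is one day short of the synopsis maximum (4 − 3 = 1). No Friday case is needed: a patient recruited in the evening who starts the next day already exceeds it.

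**3. Count the Friday case.** This assumes that the three study days are consecutive.

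| Calendar day | Fri | Sat | Sun | Mon | Tue | Wed |
|---|---|---|---|---|---|---|
| Count | 1 | 2 | 3 | 4 | 5 | 6 |
| Event | enrolment | – | – | baseline | rTMS | follow-up |

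That is 6 calendar days, or 5 elapsed, and 6 / 3 = 2 times the figure in Question 3. If Friday is the screening visit, there are four visit days. The synopsis figure therefore still holds as a count of measurement days, but not as a span of participation.

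**4. Check the screening window in 8.1.** The permitted gap from screening to inclusion is 0 or 1 day. Suppose screening is done on Friday:

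| Meaning of inclusion | Gap | Within window? |
|---|---|---|
| Friday enrolment | 0 days | yes |
| Monday study start | 3 days | no |

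The word enrolment in the Friday note favours the first reading. The schedule column that joins enrolment with baseline assessment favours the second. If screening itself takes place on Monday, which the floating screening day allows, there is no gap.

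**5. Follow the cross-reference.** Section 2 runs from 2.1 to 2.2.3 and is followed by section 3, so there is no 2.3.1. The title quoted in the note, Known Potential Risks, belongs to 2.2.1, and section 5.3 cites it under that number. Section 2.2.1 does not mention the weekend.

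**6. How many patients.** The documents give no enrolment figures by weekday. As an illustration only, even enrolment over five weekdays would give 40 × 1/5 = 8 patients on the Friday path.

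**The case against.** The fairest defence is that three days is a count of study days from baseline, as in section 5.3, with screening left out. That probably explains the figure. It does not rescue Question 3, because patients consent at Visit 1, the synopsis counts up to four days, and the question gives no counting rule.

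A second defence is that section 5.5 presents the form as an example of part of the review, with an obviously wrong alternative, and that the full consent form cannot be seen here. What patients are finally told may be correct. This limits the claim to the text shown, but neither option there matches the synopsis. Friday patients also make a separate declaration about the weekend, so it is put to them. That softens the consequence without making the stated length right.

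Three stronger readings are tempting, and the documents do not support them:

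- *The Friday rule definitely breaks the screening window.* It does so only if screening is done on Friday and inclusion means the Monday start. The text settles neither.
- *The anchor of the Hallucination Change Scale (HCS) is out of date for Friday patients.* The synopsis places the baseline HCS at the first visit, but the schema puts it at Visit 2, and section 3 anchors it on the preceding 24 hours. Nothing says that it is taken before the weekend. The two labels should simply agree.
- *The weekend lies outside safety cover.* The three-day phrase occurs in one sentence of 2.2.1. Sections 5.5 and 7.2 do not limit antipsychotic use for a worsening patient to three days, and 8.3.4 records events from consent onward. Section 2.2.1 gives the voices questionnaire at every visit, and 7.2 checks for medication changes before each one.

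**Conclusion.** The statements of study length are wrong as written. Question 3 has patients affirm at most 3 days. The synopsis allows 4, and the Friday rule spans 6 calendar days on the assumption of consecutive visits. The three-day wording in 2.2.1 has the same fault, and the reference to 2.3.1 leads nowhere.

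The conflict with 8.1 is conditional: 3 days against a limit of 1 on one reading of inclusion, and none on the other. The ambiguity is the defect there.

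Two assumptions remain. The answer key to Question 3 is inferred from the alternative of three weeks, and the sample question is taken to reflect the form in use. The figure of 8 patients is an illustration and carries no weight in the conclusion. This is an inconsistency in what patients affirm before consent and in the schedule. It is not evidence of missing protection or of a biased primary outcome.

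**What to change.** 1. Reconcile sections 1.1, 1.3, 2.2.1, 5.5 (Question 3 and the note under the compensation table) and 8.1 to one schedule, and say whether days are counted as visit days or calendar days.
2. Have Question 3 state the longest period that the schedule allows from consent to the last visit, including the weekend if the Friday path is kept.
3. Define inclusion in 8.1, and say whether Friday enrolment is an exception to the screening window.
4. Align the first-visit label for the baseline HCS in the synopsis with Visit 2 in the schema.
5. Correct the reference from 2.3.1 to 2.2.1 in both places, and make the wording of 2.2.1 consistent with the reconciled schedule, including the weekend.

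Which schedule stands, and any rule on medication, monitoring or termination, is for the investigators to decide. The cost is wording changes and ethics board approval of the revised question. No visit, rating or analysis needs to be added.
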